1. STUDY DESIGN

- 1.1. *Study Overview.* This study will use a two-arm randomized study design. Participants will be recruited across three cancer types. Each of the participants will be randomized to an active “intervention” arm (using the full SYNC app) or to a control arm (using a “dummy” version of the SYNC app that gives recommendations for light at times that should not significantly affect the circadian clock). The random allocation of participants to the treatment arm or control arm establishes the basis for testing the statistical significance or difference between the groups in the measured outcome (patient fatigue, assessed by a daily 1-question fatigue survey and the PROMIS 4-item Fatigue). Patient age, gender, and other prognostic baseline characteristics that could potentially confound an observed association, including those that are unknown or unmeasured, will be distributed equally, except through chance alone, through random assignment. Thus, this design is well-suited to our goal of assessing the efficacy of a mobile health intervention, SYNC, on participants.
- 1.2. *Primary Hypothesis.* The primary hypothesis is that a mobile-app delivered circadian intervention (SYNC) will reduce patient fatigue.
- 1.3. *Study Objectives*
 - 1.3.1. Primary Objective. To test the difference between the “intervention” (full SYNC app) arm and the control (limited SYNC app) arm in the measured outcome of patient fatigue, assessed by daily 1 question surveys and weekly 4-item PROMIS questionnaires over the course of 12 weeks.
 - 1.3.2. Secondary Objective. To determine the change in sleep disturbances, anxiety, depression, physical functioning, and global health through PROMIS questionnaires, between baseline and the 12-week assessment in both the control and intervention arms, and to look for differences in this change between the two arms.
 - 1.3.3. Exploratory Objectives
 - 1.3.3.1. Change in patient physical activity through physiological data capture using the wearable sensors in the control versus intervention arm.
 - 1.3.3.2. Change in patient health care utilization (e.g., total count of hospital days, readmissions, and ambulatory care clinic visits) in the control versus intervention arm
 - 1.3.3.3. Change in patient sleep aid usage in the control versus intervention arm.
- 1.4. *Participant Eligibility*
 - 1.4.1. Inclusion Criteria

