3. STUDY ENDPOINTS

3.1. *Primary Endpoint.* The primary endpoint is **fatigue**, as assessed by a daily fatigue questionnaire and a weekly 4-item PROMIS fatigue questionnaire.

3.2. *Secondary Endpoint.* The secondary endpoints are sleep disturbance, anxiety, depression, physical function and global health, as measured via the following PROMIS validated instruments:

- PROMIS Sleep Disturbance (8-item)
- PROMIS Anxiety (7-item)
- PROMIS Depression (8-item)
- PROMIS Physical Function (8-item)
- PROMIS Global Health (10-item)

3.3. *Exploratory Endpoints.*

3.3.1. Activity data. Patient activity (steps) and sleep will be measured continuously from the start to the end of the trial through wearable sensors.

3.3.2. Health care utilization data. Patient health care utilization data (e.g., total count of hospital days, emergency department visits, readmissions, and ambulatory care clinic visits) will be captured through the electronic health record as well as self-report (i.e., if the patient is readmitted at an outside hospital other than Michigan Medicine).

3.3.3. Sleep aid utilization data will be collected via self-report in the app once a week.

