- 5.6. *Primary Endpoint.* The primary objective of the study is to test the effects of SYNC in a randomized controlled clinical trial design. Patients will be randomly assigned to the treatment arm or the control arm. The primary objective is to quantify the effects of the light interventions delivered by SYNC on patient fatigue.
- 5.7. *Sample Size Considerations.* We will enroll 138 cancer patients, with half in the intervention arm and half in the control arm. Our primary endpoint is the PROMIS 4-item Fatigue Short Form. The age- and sex-adjusted norm for the Fatigue scale is 50 points, with a standard deviation of 10 points. These statistics have been shown to be largely generalizable to the cancer patient population (mean: 52, standard deviation 7.6). Our study will have power of 0.80, assuming a two-sided Type I error rate of 0.05, to detect an effect size of half the standard deviation between the intervention and control arms if 64 cancer patients are enrolled in each of the control and intervention groups. A mean difference of one-half a standard deviation is clinically meaningful and is considered a medium effect size for clinical trials. During the primary analysis, we will adjust for the fact

that there are three cancer populations in our data and will look for a well-defined effect that is marginal within each population. We will accrue a total of 69 patients in each arm to account for attrition of data, assuming a 7% dropout rate from the trial.

5.8. PROMIS® measures use Item Response Theory (IRT), a family of statistical models that link individual questions to a presumed underlying trait or concept of global health represented by all items in the scale. PROMIS® instruments are scored using item-level calibrations. The most accurate way to score a PROMIS® instrument is to use the Health Measures Scoring Service, which our Study Team has experience with. This method of scoring uses “response pattern scoring,” which uses responses to each item for each participant. Response pattern scoring is especially useful when there is missing data (i.e., a respondent skipped an item), or different groups of participants responded to different items).

There are four key features of the score for PROMIS® Fatigue:

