5.12. *Analysis of Primary Endpoint.* Analysis will be an intent-to-treat analysis that includes all participants. Mean Global Health scores at the end of the trial will be compared using a two-sample *t*-test (or Wilcoxon Rank Sum test if non-normality is apparent) with a significance level of 0.05. Linear regression models will be performed to complement the results of the *t*-test and adjust for specific baseline participant's characteristics (e.g., demographic, social, environmental) to increase the precision of our inference. There is a possibility that patient characteristics will be unbalanced since our randomization scheme will be applied to participants. Thus, our models also will assess potential moderating or mediating effects.

5.13. *Analysis of Secondary Endpoint.*

Mean PROMIS scores (PROMIS sleep disturbances, anxiety, depression, physical function, and global health) for each arm at the end of the trial will be compared using a two-sample *t*-test (or Wilcoxon Rank Sum test if non-normality is apparent) with a significance level of 0.05. Linear regression models will be performed to complement the results of the *t*-test and adjust for specific baseline participant's characteristics (e.g., demographic, social, environmental) to increase the precision of our inference. There is a possibility that patient characteristics will be unbalanced since our randomization scheme will be applied to participants. Thus, our models also will assess potential moderating or mediating effects.

5.14. *Analysis of Exploratory Endpoints.*

5.14.1. Patient activity. The accelerometer data of each subject will be transformed into a low-dimensional representation using motif discovery algorithms.⁷⁹ Such techniques are completely data-driven, and search for motifs (i.e., patterns) in the data that occur more often than chance. A signal can then be represented by the number of times a particular motif occurs. Others have successfully used such techniques for representing a variety of waveform data, including accelerometer and continuous glucose data.⁸⁰⁻⁸² The accelerometer data will be processed to derive estimates of total sleep duration (i.e., hours per night), wake after sleep onset, and sleep efficiency (i.e., ratio of sleep to wake). The variables will be compared between arms.

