Global03	In general, how would you rate your physical health?	 5	 4	 3	 2	 1
Global04	In general, how would you rate your mental health, including your mood and your ability to think?	 5	 4	 3	 2	 1
Global05	In general, how would you rate your satisfaction with your social activities and relationships?	 5	 4	 3	 2	 1
Global06	In general, please rate how well you carry out your usual social activities and roles. (This includes activities at home, at work and in your community, and responsibilities as a parent, child, spouse, employee, friend, etc.).....	 5	 4	 3	 2	 1
Global08	To what extent are you able to carry out your everyday physical activities such as walking, climbing stairs, carrying groceries, or moving a chair?	 5	 4	 3	 2	 1

In the past 7 days...

		Never	Rarely	Sometimes	Often	Always						
Global09	How often have you been bothered by emotional problems such as feeling anxious, depressed or irritable?	 5	 4	 3	 2	 1						
Global08	How would you rate your fatigue on average?	 5	 4	 3	 2	 1						
Global07	How would you rate your pain on average?	 0 No pain	 1	 2	 3	 4	 5	 6	 7	 8	 9	 10 Worst pain imaginable

Morningness-Eveningness Questionnaire:

1. One hears about “morning” and “evening” types of people. Which one of these types do you consider yourself to be?
 - a. Definitely a morning type
 - b. More of a morning than evening type

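### The primary-endpoint analysis in 5.12 tests PROMIS Global Health, so as written no test of fatigue, the primary endpoint, is specified

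*Combined protocol and SAP*

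**What the plan says.** The intent is stated many times and always concerns fatigue. The Study Design section says: "The primary hypothesis is that a mobile-app delivered circadian intervention (SYNC) will reduce patient fatigue". Section 5.6 says: "The primary objective is to quantify the effects of the light interventions delivered by SYNC on patient fatigue". Section 3.1 defines the primary endpoint as fatigue, "as assessed by a daily fatigue questionnaire and a weekly 4-item PROMIS fatigue questionnaire". The sample size section, 5.7, is narrower: "Our primary endpoint is the PROMIS 4-item Fatigue Short Form".

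Section 5.12, headed as the analysis of the primary endpoint, then names a different variable: "Mean Global Health scores at the end of the trial will be compared using a two-sample" t-test, or a Wilcoxon rank sum test if the data look non-normal, at the 0.05 level. The regression models in the same section are there to complement that t-test.

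Global Health has its own place elsewhere. Section 3.2 says: "The secondary endpoints are sleep disturbance, anxiety, depression, physical function and global health". Section 5.13 analyses "Mean PROMIS scores (PROMIS sleep disturbances, anxiety, depression, physical function, and global health) for each arm at the end of the trial" by the same method. Fatigue is not in that list, nor among the exploratory analyses in 5.14.

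**The concern.** A primary analysis should test the variable that the hypothesis, the endpoint definition and the sample size all refer to. Here the variable changes in the one section that fixes the test. Global Health ends up analysed twice and fatigue not at all.

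Two things are at stake. First, if 5.12 is followed literally, the confirmatory p-value belongs to another construct: a 10-item scale in which a single item asks about fatigue ("How would you rate your fatigue on average"), and on which no effect size or standard deviation has been justified.

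Second, if the team repairs the slip late, it must choose what to put in its place. Two instruments are candidates (the daily item and weekly PROMIS Fatigue 4a), the time point for fatigue is not fixed, and a single 0.05 is stated without a rule for two instruments. Section 5.5 says the investigators and study team cannot be blinded, so a choice made after data have accrued would be open to the charge of having been guided by them.

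**Working it through.** **1. What each section names**

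| Place | Variable |
|---|---|
| Synopsis, primary objective | Fatigue: daily survey and weekly PROMIS Fatigue 4a |
| Synopsis, accrual objective | PROMIS Fatigue 4-item form alone |
| Study Design 1.2 and 1.3.1 | Fatigue; 1.3.1 names both instruments, over 12 weeks |
| 3.1 | Fatigue, both instruments |
| 3.2 | Global Health listed as secondary |
| 5.6 | Fatigue |
| 5.7 | PROMIS Fatigue 4-item form alone |
| **5.12 (primary test)** | **Global Health, end of trial** |
| 5.13 (secondary tests) | Sleep disturbance, anxiety, depression, physical function, Global Health |
| 5.14 (exploratory) | Activity and sleep, health care use, sleep aids |

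No row gives a between-arm test of either fatigue instrument. Section 5.7 says that the primary analysis will adjust for the three cancer populations, but it names no model or time point.

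**2. The plan's own sample size.** Inputs from 5.7: two-sided alpha 0.05, power 0.80, effect 0.5 SD.

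- Normal approximation: n = 2(1.960 + 0.842)² / 0.5² = 62.8, so 63 per arm.
- Noncentral t: n = 63.77, so 64 per arm; power at 64 per arm is 0.801.
- Dropout of 7%: 64 / 0.93 = 68.8, so 69 per arm and 138 in total.

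The stated figures reproduce. They are framed entirely on PROMIS Fatigue.

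**3. Power of the test that 5.12 describes.** The documents give no effect size for Global Health, so the effects below are assumptions. Two-sample t-test, 64 per arm, two-sided 0.05:

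| Assumed effect on Global Health (SD) | Share of 0.5 SD | Power |
|---|---|---|
| 0.50 | 100% | 0.80 |
| 0.375 | 75% | 0.56 |
| 0.25 | 50% | 0.29 |
| 0.125 | 25% | 0.11 |

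A lower-bound scenario: only the one fatigue item moves, by 0.5 SD, in an equally weighted sum of ten items with equal variances and a common inter-item correlation ρ. Then d = 0.5 / √(10 + 90ρ).

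- ρ = 0.3: 0.5 / √37 = 0.082, power 0.075
- ρ = 0.5: 0.5 / √55 = 0.067, power 0.067
- ρ = 0.7: 0.5 / √73 = 0.059, power 0.062

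**4. Two fatigue instruments at 0.05 each.** This applies if success on either one would count.

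- Independent tests: 1 − 0.95² = 0.0975.
- Correlated test statistics (bivariate normal, assumed correlations): 0.0907 at 0.5 and 0.0781 at 0.8.

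**The case against.** The strongest reply is that this is a one-noun drafting slip. The heading of 5.12, objective 1.3.1 and sections 5.6 and 5.7 all make clear that fatigue was meant, and 5.7 names the instrument, the alpha and an adjusted primary analysis. That is very likely how the error arose. But knowing the intent does not supply a test: none of those sections fixes a method and a time point, and they disagree on whether one or two instruments are primary.

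The power figures draw fair criticism too.

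- The sample size is in SD units, so 0.80 power at 0.5 SD would hold for any continuous score. What stands is that 0.5 SD is argued for fatigue and for nothing else.
- The one-item scenario is artificial. The protocol expects gains in sleep and quality of life, Global Health asks about quality of life directly, 5.8 prefers item-response scoring to a simple sum, and the pain item has a different range and runs in the opposite direction before recoding. It is a floor, and the conclusion does not need it.
- The family-wise figure depends on a success rule that the plan does not state.

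Nothing shows that a correction would come after anyone has looked at outcomes, and 5.9 plans no interim efficacy analysis. The post hoc risk is therefore conditional, and an early correction removes it.

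Finally, the week-12 fatigue score needs care. The Time and Events Table gives fatigue weekly from day 1 and leaves it out of the first-and-last-day battery. Twelve weekly surveys would end on day 1 + 7 × 11 = 78; a survey on day 85 is not explicit. That calls for a fuller fix and does not weaken the point.

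**Conclusion.** The concern holds. As written, 5.12 tests a secondary endpoint under the primary heading, and no section tests fatigue, so following the plan exactly leaves the primary hypothesis without a confirmatory test. This rests on the text alone and on no numerical assumption.

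The size of the power loss cannot be read from the documents. Under the assumed Global Health effects of one quarter to three quarters of the fatigue effect, power falls from 0.80 to between 0.11 and 0.56. The split between two fatigue instruments is a smaller, related gap, worth at most a family-wise error of 9.75% if either could carry the claim. The sample size calculation itself is sound. The error must be corrected before the data are analysed.

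**What to change.** - In 5.12, replace Global Health as the tested variable with the PROMIS Fatigue Short Form 4a T-score at the week-12 assessment.
- Name that score as the single primary endpoint in the synopsis, in Study Design 1.3.1 and in 3.1. Section 5.7 already names the instrument and needs only the time point.
- Make the daily one-item fatigue survey a secondary endpoint and add it to 3.2 and 5.13. This removes the need to share the 0.05.
- Keep Global Health in 5.13 only.
- Two additions complete the repair. State which weekly survey counts as week 12 and its window, consistent with the two-week allowance in 4.4. Carry the adjustment for the three cancer populations promised in 5.7 into the model in 5.12.

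The cost is protocol and SAP wording, with at most a clarification of the survey schedule. Fatigue is already collected weekly, and the sample size stays at 64 evaluable and 69 enrolled per arm.

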Accrual Objective: We will enroll 138 cancer patients, with half in the intervention arm and half in the control arm. Our primary endpoint is the PROMIS 4-item Fatigue Short Form. The age- and sex-adjusted norm for the Fatigue scale is 50 points, with a standard deviation of 10 points. These statistics have been shown to be largely generalizable to the cancer patient population (mean: 52, standard deviation 7.6). Our study will have power of 0.80, assuming a two-sided Type I error rate of 0.05, to detect an effect size of half the standard deviation between the intervention and control arms if 64 cancer patients are enrolled in each of the control and intervention groups. A mean difference of one-half a standard deviation is clinically meaningful and is considered a medium effect size for clinical trials. During the primary analysis, we will adjust for the fact that there are three cancer populations in our data and will look for a well-defined effect that is marginal within each population. We will accrue a total of 69 patients in each arm to account for attrition of data, assuming a 7% dropout rate from the trial.

Accrual Period: The estimated accrual period is 1.5 years

Study Duration: Data will be collected from participants for 12 weeks. Passive collection of wearable data through the app will continue for up to one year for each participant who opts-in to continue using the app, and medical records may be accessed for up to five years after the conclusion of the 12-week collection period.

STUDY SCHEMA: SCHEDULE OF EVENTS

[figure not shown]

Diagram outlining the survey data collected over the trial. Note: "Control actions" here refers to following "dummy" lighting recommendations that are minimally expected to affect the circadian clock.

TIME AND EVENTS TABLE

Patient Events Timeline			
Every day after starting the trial:	Every week, starting on the first day of the trial:	On the first day and last day of the trial:	At any point in time:
Single question daily fatigue survey	PROMIS Fatigue survey, "How is your experience with the app?" questionnaire, sleep aid usage survey	PROMIS Sleep, Anxiety, Depression, Physical Function, Global Health	App experience free response

Study Timeline	Year 1				Year 2			
	Q1	Q2	Q3	Q4	Q1	Q2	Q3	Q4
Revise the app to include the capacity to collect survey responses	X	X						
Begin identifying potential subjects using UofM Health Research website		X						

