5. STATISTICAL CONSIDERATIONS

- 5.1. *Study Design.* The clinical trial is a two-arm randomized controlled trial. After completion of the intervention, data analysis will be conducted according to the statistical analysis plan outlined below. Descriptive statistics will be performed prior to conducting the statistical analyses. An intention-to-treat (ITT) analysis of the results will be based on the initial assignment of the randomized participants. With the ITT approach, participants will be analyzed according to the treatment assignment, even if the participant drops out of the study. The ITT approach minimizes biased comparisons among the treatment arms. Missing data will be imputed using the last collected data from the subject prior to dropout.
- 5.2. *Accrual.* It is estimated that 18-months will be necessary to enroll the targeted sample size. Accrual will be reported by race, ethnicity, gender, and age.
- 5.3. *Study Duration.* Survey results and wearable data will be actively collected from participants over the course of 12 weeks. At the conclusion of the 12 weeks, passive collection of wearable data through the app will continue for up to one year for each participant who opts-in to continue using the app. Medical records may be accessed for up to five years after the conclusion of the 12-week collection period.
- 5.4. *Randomization.* Blocked randomization will be used to limit bias and achieve an equal distribution of participants to the intervention and control arms of the study (69 randomized, 69; with 23 from each cancer population in each arm). This approach will recruit participants in small blocks to ensure that half of the participants within each block will be allocated to the treatment and the other half to the control. The size of the blocks will be permuted to limit selection bias, and within each block, the order of patients will be random. The study statistician will create a randomization list before the study begins enrollment using the statistical package R. This list will be used by the study group in assigning patients to the correct study arm.
- 5.5. *Blinding.* Study arm assignments cannot be blinded to the investigators or the rest of the study team because it will be known whether participants have SYNC on their mobile device or not (due to technical purposes).

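### Section 5.12 does not specify the population-adjusted primary analysis promised in 5.7: its only test with a significance level is unadjusted, and its regression names neither cancer population nor baseline fatigue

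*Combined protocol and SAP*

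**What the plan says.** - **5.7, Sample Size Considerations**, commits the main analysis to an adjustment: "During the primary analysis, we will adjust for the fact" that there are three populations. The Accrual Objective in the synopsis says the same, "During the primary analysis, we will adjust for the fact that there are three cancer populations in our data", and adds that the team "will look for a well-defined effect that is marginal within each population".
- **5.12, Analysis of Primary Endpoint**, describes something else: "Mean Global Health scores at the end of the trial will be compared using a two-sample" t-test, or a Wilcoxon test if the data look non-normal, at 0.05. After that, "Linear regression models will be performed to complement the results of the" t-test. The covariates are baseline characteristics given only as examples: "e.g., demographic, social, environmental) to increase the precision of our inference". The models are also to look at moderating or mediating effects. No significance level or primary status is given to any regression.
- **5.12** also states: "Analysis will be an intent-to-treat analysis that includes all participants". **5.11.1** limits the primary population to those who completed the baseline measures.
- **5.13** repeats the 5.12 wording for the secondary scales.
- **5.4** sets the target allocation, "with 23 from each cancer population in each arm".
- **The Time and Events Table** schedules PROMIS Fatigue weekly from the first day, so a baseline score exists.

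**The concern.** The section that should define the primary analysis does not contain the analysis that the sample size section says will be done. No other section states the adjusted model. An unadjusted t-test, a population-adjusted regression, or a regression on some other set of baseline characteristics could each be reported as consistent with the plan, and the choice could be made after the data are seen. Section 5.5 says the study team is not blinded to arm, which gives more reason to fix the choice in advance.

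A second, lesser matter is efficiency. Cancer population and first-day Fatigue 4a are both already collected, and the only test with a stated level uses neither.

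**Working it through.** **1. The texts side by side.** 5.7: the primary analysis adjusts for population. 5.12: the test at 0.05 adjusts for nothing, and the regression is a complement with an open list. The two can be made to agree only by assuming that population is among the unnamed covariates and that the complementary regression is the primary analysis. Neither is stated.

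**2. The plan's own figure.** Inputs from 5.7: two-sided 0.05, effect d = 0.5 SD, 64 evaluable per arm, 7% dropout. For an unadjusted t-test the noncentrality is d × √(n/2) = 0.5 × √32 = 2.83 with 126 df, giving power 0.801. At 63 per arm it is 0.795, so 64 is the smallest adequate size. Then 64/0.93 = 68.8, which rounds up to 69. The sample size is reproduced; it is the size for the unadjusted test.

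**3. Population as covariate (promised).** The share of outcome variance explained by population, R², is not in the documents; 1% to 10% is assumed. The effect becomes 0.5/√(1 − R²), with 124 df and 64 per arm, assuming populations are balanced across arms.

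| R² | effect | power |
|---|---|---|
| 0.01 | 0.503 | 0.805 |
| 0.05 | 0.513 | 0.821 |
| 0.10 | 0.527 | 0.841 |

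**4. First-day Fatigue 4a as a further covariate (not promised).** The correlation r between baseline and end of trial is also assumed. The effect becomes 0.5/√(1 − r²), with 123 df, population terms in the model but explaining nothing.

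| r | effect | power |
|---|---|---|
| 0.3 | 0.524 | 0.837 |
| 0.5 | 0.577 | 0.900 |
| 0.7 | 0.700 | 0.976 |

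**5. Allowance for the entry criterion.** Study Design 1.4.1.6 requires a screening fatigue rating of at least 4, which may narrow the baseline range and so weaken r. Assume, for illustration, normal scores, a cut at the mean of the screening item, and correlation q between that item and baseline 4a. Baseline variance shrinks to v = 1 − q² × 2/π, and r becomes r√v / √(1 − r² + r²v). The effect is held at 0.5 SD of the outcome in enrolled patients.
- q = 0.7: v = 0.688; r falls to 0.252, 0.432, 0.631; power 0.826, 0.875, 0.951.
- q = 1 (4a itself truncated): v = 0.363; r falls to 0.186, 0.329, 0.509; power 0.815, 0.844, 0.903.

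**6. Validity of the t-test.** If arms are balanced within population, the t-test slightly overstates its standard error. Its approximate true level is 2{1 − Φ(1.96/√(1 − R²))} = 4.9%, 4.4% and 3.9% at R² of 1%, 5% and 10%. It does not exceed 5%.

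**7. Effects within each population.** At the 5.4 target of 23 per arm, power for 0.5 SD is 0.38. At 21 per arm (64/3 = 21.3) it is 0.35. The 95% CI half-width is about 0.59 to 0.62 SD. These can be estimates only.

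**The case against.** The best defence is that 5.7 and 5.12 should be read together. The covariate list in 5.12 consists of examples, so it excludes neither population nor baseline fatigue, and the models for moderating effects are a natural place for effects by population. On that reading only detail is missing. This stands in part: a reader might infer that 5.12 rules population out, and it does not. But an open list under a complementary analysis neither delivers a commitment made for the primary analysis nor says which result decides.

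It can also be said that little is at stake numerically. The promised adjustment is worth 0 to 4 points of power; the larger gains come from baseline fatigue, which no section promises for the primary analysis, and they rest on assumed correlations. That stands. Baseline adjustment is a recommendation here, not a contradiction.

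A reader might further infer that 5.13 contradicts the secondary objective (Study Design 1.3.2), which asks about differences in change. It does not: under randomization, end-of-trial means and changes from baseline estimate the same arm difference, so only efficiency is affected.

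Finally, Study Design 1.3.1 speaks of weekly questionnaires over 12 weeks, so a repeated-measures model could also be justified. ANCOVA is proposed because it stays closest to the end-of-trial comparison already in 5.12. What matters most is that one model is named.

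**Conclusion.** The point holds as a gap in pre-specification. The plan promises an adjustment that its analysis section does not specify, and it does not identify the result that answers the primary question. It would be wrong to conclude that the trial is underpowered or that the t-test is biased: planned power is 0.80 at 64 per arm, and the test keeps its level.

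Under the assumptions in the working, the promised adjustment moves power from 0.80 to between 0.805 and 0.841. Adding first-day Fatigue 4a gives 0.84 to 0.98, or 0.82 to 0.95 across the two range-restriction cases. The textual finding depends on none of these assumptions; only the size of the gain does. It should be corrected before data lock, but the trial remains valid without it.

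The reference to Global Health in 5.12, the question whether blocks in 5.4 are formed within population, and the carrying forward of last values in 5.1 are separate issues.

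**What to change.** In 5.12:
- Make the primary test a linear model (ANCOVA) of the end-of-trial Fatigue 4a T-score on arm, cancer population (three levels) and first-day Fatigue 4a, at two-sided 0.05. Keep the t-test as supporting.
- State which weekly form counts as end of trial. Weekly forms from day 1 fall on days 78 and 85, either side of day 84. If the two-week allowance in 4.4 is meant to cover this form, say so; the form has a seven-day recall.
- Report the arm effect in each population with a 95% CI and no test. The moderating-effect models already foreseen can carry this.
- Require the baseline score to be completed before the app's recommendations begin. This agrees with 4.3, which places the PROMIS baseline before the intervention, and with Study Design 1.5.5, which places it after randomization.
- Reconcile 5.11.1 (baseline completers) with 5.12 (everyone). If everyone is kept, one simple rule for the few missing baselines is enough, for example the mean baseline score of the patient's cancer population, provided it uses no arm or post-baseline data.

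Optionally, use the same model in 5.13 with each scale's own first-day score.

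The cost is SAP wording and one standard model. The covariates are already collected, and sample size and assessments do not change.

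### Five secondary PROMIS scales are each tested at 0.05 with no error control or link to the primary result: about a 15–23% chance of some false difference, and about 7–12% of a false benefit

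*Combined protocol and SAP*

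**What the plan says.** Section 3.2 lists the secondary family without ranking it: "The secondary endpoints are sleep disturbance, anxiety, depression, physical function and global health". Section 5.13 takes the same five, "Mean PROMIS scores (PROMIS sleep disturbances, anxiety, depression, physical function, and global health) for each arm at the end of the trial", and compares each between arms by a two-sample t-test, or a Wilcoxon rank sum test if the data look non-normal, "with a significance level of 0.05". Covariate-adjusted regressions are added to complement those tests.

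Section 5.12 sets the same 0.05 level for the primary analysis, but the score it names for that comparison is Global Health. Sections 3.1 and 5.7 make fatigue the primary endpoint, and 5.7 specifies the 4-item PROMIS Fatigue form. Sidedness appears only in the sample size text (synopsis and 5.7): "assuming a two-sided Type I error rate of 0.05".

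The exploratory analyses in 5.14 carry no significance level. Section 5.9 rules out interim analyses for efficacy or futility, so no error is spent over time.

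**The concern.** Each of the five scales has its own 0.05 test, and nothing limits what may be said when one of them crosses the line. No scale comes first, no level is shared, and no condition ties a secondary claim to the fatigue result. The plan does separate a secondary tier with a significance level from an exploratory tier without one, so on its face the secondary comparisons are significance tests and not descriptions.

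The synopsis describes the study as assessing whether the app reduces fatigue and improves quality of life. If fatigue does not move but one scale out of five does, that scale could be presented as a statistically significant gain on the second part. The error rate behind such a statement is that of the best of five tests, not of one.

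**Working it through.** **Inputs.** Five scales (3.2, 5.13); 0.05 per test (5.13); two-sided testing, carried over from 5.7 as an assumption because 5.13 is silent; 64 evaluable per arm and 0.5 SD (5.7). The document gives no correlation between scales, so a common correlation ρ is assumed and varied.

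**The plan's own figure first.** Section 5.7 gives 0.80 as the power for a 0.5 SD difference at two-sided 0.05, "if 64 cancer patients are enrolled in each of the control and intervention groups".
- Normal approximation: n = 2(1.960 + 0.842)²/0.5² = 62.8, so 63 per arm.
- t distribution: 63.8, so 64 per arm, with power 0.801 at 64.
- Dropout of 7%: 64/0.93 = 68.8, so 69 per arm.

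The stated numbers reproduce. The document states no family-wise figure for the secondary scales.

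**Independent scales, ineffective app.**
- At least one significant difference, either direction: 1 − 0.95⁵ = 0.226.
- At least one significant benefit: a two-sided 0.05 test leaves 0.025 in the favourable tail, so 1 − 0.975⁵ = 0.119.
- Upper bound for benefit under any correlation: 5 × 0.025 = 0.125.

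**Correlated scales.** With c = 1.96, the either-direction rate is

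1 − ∫ [Φ((c − √ρ·u)/√(1−ρ)) − Φ((−c − √ρ·u)/√(1−ρ))]⁵ φ(u) du.

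For benefit only, drop the second Φ term.

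| Assumed ρ | Either direction | Benefit |
|---|---|---|
| 0 | 22.6% | 11.9% |
| 0.3 | 20.9% | 10.5% |
| 0.5 | 18.3% | 9.1% |
| 0.7 | 14.8% | 7.4% |
| 0.8 | 12.7% | 6.4% |
| Single test | 5% | 2.5% |

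Simulated t-tests with 64 per arm agree. At ρ = 0, 0.3, 0.5 and 0.7 they give 22.2%, 21.0%, 17.9% and 14.9% in either direction, and 11.6%, 10.6%, 8.8% and 7.6% for benefit.

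**Relative inflation for ρ from 0.7 to 0.** Either direction: 14.8/5 = 3.0 to 22.6/5 = 4.5. Benefit: 7.4/2.5 = 3.0 to 11.9/2.5 = 4.8.

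**If Global Health is the primary comparison (5.12 read literally).** Four scales remain: 1 − 0.95⁴ = 0.185 in either direction and 1 − 0.975⁴ = 0.096 for benefit, if independent.

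**Price of Holm.** Its first step tests at 0.05/5 = 0.01. Power at 0.5 SD with 64 per arm goes from 0.801 to 0.585 (t distribution; 0.600 by normal approximation) for a scale that alone has an effect. If all five scales move by 0.5 SD, average power per scale under Holm is about 0.70 (normal approximation, simulated; 0.69 to 0.72 for ρ from 0.7 to 0).

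**The case against.** The strongest reply is that nothing in the document plans to claim success on a secondary scale. The primary and central hypotheses name fatigue only, and the sample size is built on fatigue. The secondary objective speaks of determining change and looking for differences, and quality of life appears in a general description in the synopsis, not in a success criterion. Whether secondary endpoints below a designated primary need formal family-wise control in a single-centre trial is partly convention, and labelling p-values nominal would answer most of the point. This stands as an argument against making Holm mandatory. It does not remove the gap: the plan sets a significance level for these tests and nowhere says that they are descriptive.

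A reader might go further and infer that the chance of a spurious *benefit* is 15–23%. The document does not support that. The only sidedness it states is two-sided, half of each test's error lies in the unfavourable direction, and the benefit rate cannot exceed 12.5% whatever the correlation. The higher range would describe benefit only if the secondary tests were one-sided at 0.05, which is nowhere stated.

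The lower end of each range is also an assumption. All five scales are self-reports by the same patients, scheduled together on the first and last day of the trial, so a correlation above 0.7 cannot be excluded. At 0.8 the rates are 12.7% and 6.4%, still more than twice those of a single test.

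Finally, a gate on the fatigue test cannot work while 5.12 specifies no fatigue test and 3.1 names two fatigue instruments. That is correct, and it sets the order of the repair.

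**Conclusion.** The concern holds at this size. For an ineffective app, two-sided tests and a common correlation between 0 and 0.7, the chance of at least one significant secondary difference is about 15–23%, and of at least one apparent benefit about 7–12%. That is roughly three to five times the single-test rates of 5% and 2.5%. With Global Health moved to the primary position, four independent scales give 18.5% and 9.6%. The freedom to switch between t-test and Wilcoxon, and the added regressions, could raise these rates; that was not quantified.

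Two further inferences would go too far. The document does not say that a win on any one scale counts as trial success; it only fails to rule out such a claim. Nor does this weakness affect the error rate of the primary test. It concerns what may be concluded from the secondary scales, and it is worth correcting because the correction is cheap.

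**What to change.** First reconcile 5.12 with 3.1 and 5.7, so that the primary test is the PROMIS Fatigue 4a score that 5.7 uses for the sample size. Then add to 5.13:

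> If the primary fatigue test is not significant, secondary scales are reported as estimates with 95% CIs and nominal p-values, without claims of significance. If it is significant, any claim of significance on a secondary scale uses the Holm procedure across the secondary family at two-sided 0.05, applied to one pre-specified p-value per scale; otherwise p-values are labelled nominal.

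The single p-value per scale has to be named, because 5.13 now allows a t-test, a Wilcoxon test and adjusted regressions. Holm is valid under any correlation, so the missing correlations are no obstacle.

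The cost is a short SAP change plus the repair of 5.12, with no new data and no change in sample size. Where a Holm claim is sought, the power loss is the one shown above: 0.80 to about 0.59 for a lone effect, and about 0.70 on average if all five scales move. A sponsor unwilling to accept that can report every secondary result as nominal, which gives up only the right to claim significance.
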